6.2. Study Drug Packaging and Labeling

For Part 1 of the study (conducted in adolescents 12 to < 18 years of age), packaging consists of HDPE bottles with white polypropylene child-resistant caps with induction seal liners, in packaging supplied by Portola Pharmaceuticals, Inc. A liquid or other formulation of betrixaban is expected to be developed and described in a future amendment to this protocol.

6.3. Study Drug Storage

Containers of capsules should be stored under Controlled Room Temperature conditions, defined as 20 to 25°C (68–77°F) in packaging supplied by Portola Pharmaceuticals, Inc.

6.4. Study Drug Preparation

Special preparation is not required. Sufficient quantities of capsules will be provided for clinical study conduct and sample retention.

6.5. Administration of Study Drug

In Part 1 of the study, the single betrixaban capsule will be taken with 240 mL of water under the supervision of study staff. Fed patients will have a light meal or snack prior to taking betrixaban. Patients will not be fed for at least 2 hours following administration of betrixaban. Patients will not have water (fluids) for 1 hour following dosing. Water volumes for Part 2 will be specified in future amendments to the protocol.

6.6. Study Drug Accountability, Handling, and Disposal

The investigator must maintain accurate records of the amounts and dates study drugs were received from Portola Pharmaceuticals, Inc. and dispensed to the patients. All drug supplies must be accounted for at the termination of the study and a written explanation provided for any discrepancies. All partially used and unused supplies must be returned promptly to Portola Pharmaceuticals, Inc. or destroyed at the site in accordance with approved written site procedures. The investigator will maintain a record of the amount and dates when unused supplies were returned to Portola Pharmaceuticals, Inc. All records will be retained as noted in Section 14.0.

7.0 STUDY CONDUCT

All procedures occurring during Part 1 of the study (administration of betrixaban in adolescents 12 to < 18 years of age) are detailed in Table 5, the Schedule of Assessments for Protocol 16-021. The patient will be domiciled in the hospital, clinical study site, or Phase 1 unit for Day 1 assessments, dosing, and through 24 hours post dose (i.e., start of Day 2). The 120-hour visit (i.e., Days 6) may be an outpatient visit. Part 1 of the study will enroll 21 adolescents 12 to < 18 years of age.

In Part 1 of the study, a total of approximately 53 to 63 mL of blood (depending on Cohort) will be drawn from each patient over a period of approximately 5 weeks. Approximately 2 mL will be drawn for each PK sample, 4.5 mL for each PD sample, and approximately 5 mL for hematology, chemistry, and coagulation samples, per local institution requirements.

This protocol will be amended prior to the commencement of Part 2 to specify age appropriate blood sampling volumes and time points.

To minimize pain and discomfort to pediatric patients during the blood sampling time points, sampling may occur via IV catheter or butterfly needle followed by saline flush. For patients with pre-existing central venous catheter or CVAD (i.e., central line, central venous line, or central venous access catheter) sampling may occur via these access points.

7.1. Screening Visit

The screening visit will take place within 30 days prior to the first dosing day. The following procedures will be completed for patients in all age categories (12 to <18 years of age, and 2 to <12 years of age):

- Obtain Informed Consent from parent or legal guardian and Assent from patient.
- Review eligibility (i.e., review Inclusion and Exclusion criteria, Sections 4.1 and 4.2).
- Obtain medical history, including concomitant medication use (past 30 days), and demographics (Section 9.1.1).
- Conduct complete Physical Examination (PE), including vital signs and body temperature (degrees Celsius [°C]), and weight (Sections 9.1.2, 9.1.3, and 9.1.4).
- Measure height in centimeters (Section 9.1.4).
- Draw blood for hematology, coagulation assessments (Section 9.1.6.1), and blood chemistry analysis (Section 9.1.6.2).
- Draw blood for serum pregnancy test (females of childbearing potential only; Section 9.1.6.6).
- Collect urine for urinalysis, include testing for blood in urine (Section 9.1.6.3).

- Collect urine sample for drug abuse screen adolescents age 12 years to <18 years. (Section 9.1.6.5).
- Collect stool samples (if available) for occult blood testing (Section 9.1.6.4).
- Conduct 12-lead ECG (Section 9.1.5).

7.2. Day -1 (the day before anticipated dosing)

The patient may check into the hospital, clinic study site, or Phase 1 unit the day before dosing with betrixaban is anticipated. The following procedures will be completed/repeated (unless performed \leq 3 days prior to Day -1 visit, for example Days -4, -3, and -2):

- Review eligibility criteria (Sections 4.1 and 4.2).
- Review medical history and update, if appropriate (Section 9.1.1).
- Obtain cohort assignment from Sponsor.
- Conduct limited PE (Section 9.1.2), including vital signs and body temperature (degrees Celsius [°C]), and weight (Sections 9.1.2, 9.1.3, and 9.1.4).
- Draw blood for hematology and coagulation assessments (Section 9.1.6.1), and blood chemistry analysis (Section 9.1.6.2).
- Draw blood for serum pregnancy test (females of childbearing potential only; Section 9.1.6.6).
- Collect urine for urinalysis, include testing for blood in urine (Section 9.1.6.3).
- Collect urine sample for drug abuse screen (Section 9.1.6.5).
- Verify negative result for fecal occult blood testing during Screening period (\leq 30 days prior to dosing). (Section 9.1.6.4).
- Record AEs since screening visit.
- Record concomitant medications since the screening visit.

7.3. Day 1 (Dosing with Betrixaban)

7.3.1. Pre-Dose Assessments and Dosing

7.3.1.1. Prior to Dosing

- Review eligibility criteria (Sections 4.1 and 4.2).
- Review medical history and update, if appropriate (Section 9.1.1).
- Review pre-dose laboratory results to confirm continued eligibility.
- Draw blood for betrixaban plasma PK analysis (Section 8.1).
- Draw blood for PD assessments, i.e., TGI and anti-fXa levels (Section 8.2).
- Obtain vital signs (sitting) and body temperature (°C) ≤ 30 minutes prior to dosing (Section 9.1.2).

- Ensure that patient does not have fluids 1 hour prior to dosing.
- Collect stool samples (if available) for occult blood testing (Section 9.1.6.4).
- Record AEs.
- Record concomitant medications.

7.3.1.2. Dosing (0.0 Hours, Day 1)

- Administer 1 betrixaban capsule with 240 mL of water (in adolescents 12 to < 18 years of age).
 - Patients will have a low-fat breakfast or snack prior to dosing (e.g., apple sauce, biscuit, fruit, crackers, or commercial nutritional supplement.).
- Ensure that patient does not have fluids 1 hour after dosing.
- Ensure that patient waits 2 hours after dosing before ingesting food; there are no post dose restrictions regarding food intake. The 2 hour PK sample will be taken before ingesting food.

7.3.2. Post Dose Procedures, Day 1

7.3.2.1. Between 0.5 Hour and 24.0 Hour Post Dose

• Collect stool samples (if available) for occult blood testing (Section 9.1.6.4).

7.3.2.2. 0.5 Hour Post Dose (Day 1)

- Obtain vital signs (sitting) and body temperature (°C) (Section 9.1.2).
- Confirm PK-PD sampling requirement (Section 8.1, Section 8.2) based on subject-specific Cohort and Sequence Assignments. Refer to Table 5, Schedule of Assessments.
- Record AEs.
- Record concomitant medications.

7.3.2.3. 1.0 Hour Post Dose (Day 1)

- Obtain vital signs (sitting) and body temperature (°C) (Section 9.1.3).
- Provide patient with fluids.
- Confirm PK-PD sampling requirement (Section 8.1, Section 8.2) based on subject-specific Cohort and Sequence Assignments. Refer to Table 5, Schedule of Assessments.
- Record AEs.
- Record concomitant medications.

7.3.2.4. 2.0 Hours Post Dose (Day 1)

- Obtain vital signs (sitting) and body temperature (°C) (Section 9.1.3).
- Confirm PK-PD sampling requirement (Section 8.1, Section 8.2) based on subject-specific Cohort and Sequence Assignments. Refer to Table 5, Schedule of Assessments.
- Meal allowable after blood sampling. There are no post dose restrictions regarding food intake after this timepoint.
- Record AEs.
- Record concomitant medications.

7.3.2.5. 3.0 Hours Post Dose (Day 1)

- Obtain vital signs (sitting) and body temperature (°C) (Section 9.1.6.1).
- Confirm PK-PD sampling requirement (Section 8.1, Section 8.2) based on subject-specific Cohort and Sequence Assignments. Refer to Table 5, Schedule of Assessments.
- Perform 12-lead ECG (Section 9.1.5)
- Record AEs.
- Record concomitant medications.

7.3.2.6. 4.0 Hours Post Dose (Day 1)

- Obtain vital signs (sitting) and body temperature (°C) (Section 9.1.6.1).
- Confirm PK-PD sampling requirement (Section 8.1, Section 8.2) based on subject-specific Cohort and Sequence Assignments. Refer to Table 5, Schedule of Assessments.
- Record AEs.
- Record concomitant medications.

7.3.2.7. 6.0 Hours Post Dose

- Obtain vital signs (sitting) and body temperature (°C) (Section 9.1.3).
- Confirm PK-PD sampling requirement (Section 8.1, Section 8.2) based on subject-specific Cohort and Sequence Assignments. Refer to Table 5, Schedule of Assessments.
- Record AEs.
- Record concomitant medications.

7.3.2.8. 12.0 Hours Post Dose

- Obtain vital signs (sitting) and body temperature (°C) (Section 9.1.3).
- Confirm PK-PD sampling requirement (Section 8.1, Section 8.2) based on subject-specific Cohort and Sequence Assignments. Refer to Table 5, Schedule of Assessments.

- Record AEs.
- Record concomitant medications.

7.4. Day 2: 24 Hours Post Dose

- Obtain vital signs (sitting) and body temperature (°C) (Section 9.1.3).
- Conduct limited PE, (Section 9.1.2); including weight.
- Draw blood for hematology, coagulation assessments (Section 9.1.6.1), and blood chemistry analysis (Section 9.1.6.2).
- Confirm PK-PD sampling requirement (Section 8.1, Section 8.2) based on subject-specific Cohort and Sequence Assignments. Refer to Table 5, Schedule of Assessments.
- Collect urine for urinalysis, include testing for blood in urine (Section 9.1.6.3).
- Record AEs.
- Record concomitant medications.
- Perform 12-lead ECG (Section 9.1.5).

7.5. Day 6: 120 Hours Post Dose (Study Termination Visit)

- Obtain vital signs (sitting) and body temperature (°C) (Section 9.1.3).
- Conduct brief PE (Section 9.1.2); including weight.
- Draw blood for hematology, coagulation assessments (Section 9.1.6.1), and blood chemistry analysis (Section 9.1.6.2).
- Confirm PK-PD sampling requirement (Section 8.1, Section 8.2) based on subject-specific Cohort and Sequence Assignments. Refer to Table 5, Schedule of Assessments.
- Collect urine for urinalysis, include testing for blood in urine (Section 9.1.6.3).
- Record AEs.
- Record concomitant medications.
- Collect stool samples (if available) for occult blood testing (Section 9.1.6.4).

7.6. Day 7: Safety Follow-up Contact

One safety follow-up phone call/contact to the patient (if appropriate), parent, or legal guardian will occur on Day 7; the following procedure will be performed:

- Record AEs.
- Record concomitant medications.

8.0 PHARMACOLOGICAL ASSESSMENTS

8.1. Pharmacokinetic Assessments

The plasma portion of the blood samples will be assayed for determining the PK parameters of betrixaban. The following PK parameters will be calculated for each age groups using POP PK methodology as long as sufficient data is available:

- Terminal plasma half-life ($t_{\frac{1}{2}}$), determined by linear regression of the log concentration on the terminal portion of the plasma concentration–time curve. Half-life is calculated as $ln(2)/(-\beta)$, where β is the slope of the terminal portion of the log concentration–time curve.
- Time to maximum observed plasma concentration (T_{max}).
- Maximum observed plasma concentration (C_{max}).
- Area under the plasma concentration-time curve from 0 to last available measurable concentration (AUC_(0-last)) computed using the linear trapezoidal rule.
- Clearance (CL/F), calculated by dividing the administered dose by the AUC_(0-∞).
- Volume of Distribution (V_d/F) , calculated by dividing the dose administered by the plasma concentration at the first time point measured.
- Total area under the plasma concentration-time curve from time 0 to infinity (total AUC), computed as:
 - Total AUC $(AUC_{(0-\infty)}) = AUC_{(0-last)} + Cp_{last} / (-\beta)$ where $AUC_{(0-last)}$ is the area under the curve from time 0 to the time point of the last measurable concentration above the quantitation limit; Cp_{last} is the last measurable concentration above the quantitation limit; and β as defined above.

8.1.1. Blood Sample Collection

Blood samples for PK analysis will be collected using 3.2% Na Citrate as the anticoagulant. Blood samples for PK assessments will be collected 30 minutes prior to the dose administration, and at 0.5, 1, 2, 3, 4, 6, 12, 24, and 120 hours post dose with the 6 hour time point only being collected in the patients with rich PK sampling. Blood samples for patients in the POP PK analysis groups will be taken at time points based on the sequences to which each patient is assigned.

8.1.2. Urine Sample Collection

Urine samples will not be collected for centralized testing.

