- Safety endpoint is the clinical assessment of AEs and other safety measurements (vital signs, ECGs, laboratory tests, etc.).

Methodology: Multiple-center, open label study of the PK, PD, and safety of a single dose of betrixaban at up to 80 mg in 33 pediatric patients who meet study entry criteria.

Following a 30-day screening period, eligible patients who have provided Assent and whose parent or legal guardian has signed an Informed Consent will receive a single, oral dose of betrixaban at 40 mg or 80 mg. The screening visit may be an outpatient visit. Patients will enter (or if hospitalized, remain in) the hospital, clinical research unit, or Phase 1 unit on Day -1, the day before dosing with betrixaban is anticipated, and remain domiciled through 24 hours after betrixaban is administered. They may undergo the remainder of procedures as outpatients, including a Day 7 follow-up safety phone call.

Part 1 (the initial opening of the study) will be conducted in 21 adolescent patients (12 to < 18 years of age) who are assessed to be at risk for VTE. Each patient will receive a single, oral, hard gelatin capsule of betrixaban. The dose administered initially to adolescent patients will be 40 mg, followed by dosing with 80 mg. The cohorts in Part 1 are defined as follows:

- Cohort 1 will enroll 3 patients (at least one of each gender), each of whom will receive a single, oral dose of betrixaban at 40 mg in the fed state, and undergo 10 PK blood sampling time points.
- Cohort 2 will enroll 18 patients (6 patients in each of 3 PK sampling sequences), each of whom will receive a single, oral dose of betrixaban at 80 mg in the fed state, and undergo 5 PK sampling time points.

After dosing, patients will undergo serial blood sampling for PK/PD evaluations. The PK and PD data from Part 1 will be used for dose determination for the next youngest age group using population PK and PBPK modeling and simulation. The primary PK parameters to be determined are $AUC_{(0-last)}$ and C_{max} . Other PK parameters to be determined are: Total AUC $(AUC_{(0-\infty)})$, $t_{1/2}$, T_{max} , CL/F, and V_d /F. All parameters will be determined per age group in a population PK type analysis except for those patients who have rich PK samples available for analysis.

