- Patient will/has receive(d) a dose of any antiplatelet medication (including aspirin) within 14 days before study drug dosing. Planned or anticipated use of antiplatelet medication (including aspirin) in the first 24 hours following dosing shall exclude the patient.
- 14. Patient has malabsorption disorders (e.g., cystic fibrosis or short bowel syndrome).
- 15. Patient has an estimated Glomerular Filtration Rate (eGFR) < 30 mL/min.
- 16. Patient is unable or reluctant to cooperate with the study procedures.
- 17. Patient has hypersensitivity to other Factor Xa inhibitors, or the components of the dosage form.
- 18. Patient has participated in a study with an investigational drug or medical device within 30 days prior to administration of betrixaban.
- 19. Patient is female and of childbearing potential and is either pregnant or breastfeeding a child.
- 20. Patient is sexually active and is not using medically accepted contraceptive method (if applicable).
- 21. Patient has positive Drugs of Abuse urine test at Screening (Part 1 subjects only) at Screening excluding medications prescribed by a physician during the current hospital stay.

Investigational product, dosage and mode of administration:

Betrixaban as either 40 mg or 80 mg hard gelatin capsules, or an oral pediatric formulation to facilitate dosing determined by weight.

Duration of treatment:

Single dose

Reference therapy, dosage and mode of administration:

None

Criteria for Evaluation:

Pharmacokinetics: Blood samples for PK analysis will be collected using 3.2% Na Citrate as the anticoagulant. Blood samples for PK assessments will be collected 30 minutes prior to the dose administration, and at 0.5, 1, 2, 3, 4, 6, 12, 24, and 120 hours post dose. The plasma portion of the blood samples will be assayed for determining the PK parameters of betrixaban for all patients in the rich PK sampling group. A subset of the samples (except the 6 hour time point) will be collected for patients assigned to each sequence in the POP PK groups. The following PK parameters will be calculated by age group using POP PK methodology, except for patients with rich PK sampling:

- Terminal plasma half-life (t¹/₂), determined by linear regression of the log concentration on the terminal portion of the plasma concentration-time curve. This will be calculated if appropriate data is available. Half-life is calculated as:

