1.0 INTRODUCTION

Betrixaban is an oral anticoagulant that is a potent and specific inhibitor of human Factor Xa (FXa), an important validated target in the blood coagulation pathway. It binds to the active site of FXa to prevent thrombosis. As the maleate salt, betrixaban has a Molecular Weight (MW) of 567.98 and is available for oral administration as an Immediate Release (IR) capsule. It is rapidly absorbed with mean peak concentrations occurring 3 to 4 hours after oral administration. Oral bioavailability of an 80 mg dose is approximately 34%, and protein binding is approximately 60%. The drug exhibits nonlinear kinetics within the expected therapeutic dosing range with greater than proportional increases in plasma concentrations occurring with increased dose; maximum plasma concentration (C_{max}) and Area Under the Curve (AUC) at steady-state increased approximately 3-fold when the dose was doubled from 40 mg to 80 mg. Excretion is mostly unchanged through the bile with renal clearance approximately 17% of the absorbed dose. When administered after a high-fat, high-calorie breakfast, C_{max} and AUC were reduced by approximately 50% as compared to the fasting state.

Betrixaban is only weakly metabolized by major cytochrome P450 enzymes. It is a substrate for efflux proteins including permeability glycoprotein (P-glycoprotein or P-gp). When co-administered with the potent P-gp inhibitor ketoconazole, betrixaban concentrations were increased more than approximately 2-fold. Based on Population Pharmacokinetic (POP PK) analysis from the Phase 2 EXPLORE Xa study (Connolly et al., 2013) [1], a similar effect was observed when betrixaban was given concomitantly with amiodarone, another strong P-gp inhibitor. A drug interaction study with the P-gp substrate, digoxin, showed no significant interaction, and one with the strong inhibitor verapamil suggests that co-administration in fasted state increases both C_{max} and exposure to betrixaban.

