After dosing, patients will undergo serial blood sampling for PK-PD evaluations (the Schedule of Assessments detailing all procedures is provided in Table 5). The PK and PD data from Part 1 will be used for dose determination for the next youngest age group using POP PK and PBPK modeling and simulation. The primary PK parameters to be determined are $AUC_{(0-last)}$ and C_{max} . Other PK parameters to be determined are Total AUC $(AUC_{(0-\infty)})$, $t_{1/2}$, T_{max} , CL/F, and V_d/F . These will be estimated using POP PK methodology for age groups except the initial group of patients for which rich PK sampling is done.

Following analysis of Part 1 data and an amendment to the protocol, Part 2 of the study will commence and enroll 12 patients 2 to < 12 years of age. Each patient will receive an open-label, single oral dose of betrixaban; these patients must be able to take either the hard gelatin capsule or an oral, liquid formulation (once it has been developed and described in a future amendment to this protocol). Similar to Cohort 2, subjects will be assigned one of two PK sampling sequences based on data from Part 1. The cohort in Part 2 is defined as follows:

• Cohort 3 will enroll 12 patients (6 patients in each of 2 PK sampling sequences), each of whom will receive a single, oral dose of betrixaban in a fed state at a dose and route to be determined, based on the analysis of Part 1 data.

After dosing, patients will undergo serial blood sampling for PK-PD evaluations.

For all cohorts, safety assessments (evaluation of AEs, concomitant medications, routine chemistries [hematology, coagulation, serum chemistries]) will occur at protocol-specified time points.

The schema of the study is depicted in Figure 1. The Schedule of Assessments for the study is provided in Table 5.

Study Part	Part 1	Part 1	Part 2 - TBD Amendment
Cohort No.	Cohort 1	Cohort 2	Cohort 3
Age	12 to < 18 years	12 to < 18 years	2 to $<$ 12 years
Dose	40 mg	80 mg	TBD
n =	3 patients (one of each gender)	18 patients (at least two of each gender)	12 patients (at least two of each gender)
PK Sampling	Rich - 10 time points	Sparse - 5 time points	Sparse – TBD time points
PK Time Points	Pre-dose, 0.5, 1, 2, 3, 4, 6, 12, 24, 120 hours	Sequence A: pre-dose, 1, 3, 12, 120 hours Sequence B: pre-dose, 0.5, 2, 4, 24 hours Sequence C: pre-dose, 2, 3, 12, 24 hours	Sequence D: TBD Sequence E: TBD

Figure 1: Schema of Study 16-021

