10.4. Determination of Sample Size

Sample size for each age group is determined by the variance for $AUC_{(0-last)}$ and C_{max} observed from the adult PK studies of betrixaban. The between-subject variability seen in $AUC_{(0-last)}$ as measured by percent coefficient of variation was around 45%. A minimum of 12 subjects are required to target a 90% confidence interval within 60% and 140% of the geometric mean estimates of the $AUC_{(0-last)}$ with at least 80% power.

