10.6. Demographics and Baseline Characteristics

Demographics and baseline characteristics will be summarized for all patients, the safety population, and the PK population. Data will be summarized using descriptive statistics such as frequencies, means, medians, standard deviations, minimums, and maximums. No formal statistical comparisons are planned.

PK Parameters Determination

The plasma level of betrixaban assessed at baseline, during the first 24 hours, and 120 hours post dosing will be used to determine the following PK parameters for each age group using POP PK methodology or for individual patients with rich PK sampling:

10.6.1. Primary PK Parameters

- AUC_(0-last)
- C_{max}

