After dosing, patients will undergo serial blood sampling for PK-PD evaluations (the Schedule of Assessments detailing all procedures is provided in Table 5). The PK and PD data from Part 1 will be used for dose determination for the next youngest age group using POP PK and PBPK modeling and simulation. The primary PK parameters to be determined are  $AUC_{(0-last)}$  and  $C_{max}$ . Other PK parameters to be determined are Total AUC ( $AUC_{(0-\infty)}$ ),  $t_{1/2}$ ,  $T_{max}$ , CL/F, and  $V_d/F$ . These will be estimated using POP PK methodology for age groups except the initial group of patients for which rich PK sampling is done.

Following analysis of Part 1 data and an amendment to the protocol, a Part 2 of the study was originally planned to commence. However, since Portola decided not to continue to develop the betrixaban program, Part 2 of this study will no longer be performed.

For both of the cohorts in Part 1, safety assessments (evaluation of AEs, concomitant medications, routine chemistries [hematology, coagulation, serum chemistries]) will occur at protocol-specified time points.

The schema of the original study design is depicted in Figure 1. Note that Part 2 will not be performed.

Study Part	Part 1	Part 1	Part 2 - TBD Amendment
Cohort No.	Cohort 1	Cohort 2	Cohort 3
Age	12 to < 18 years	12 to < 18 years	2 to $<$ 12 years
Dose	40 mg	80 mg	TBD
n =	3 patients (one of each gender)	18 patients (at least two of each gender)	12 patients (at least two of each gender)
PK Sampling	Rich - 10 time points	Sparse - 5 time points	Sparse – TBD time points
PK Time Points	Pre-dose, 0.5, 1, 2, 3, 4, 6, 12, 24, 120 hours	Sequence A: pre-dose, 1, 3, 12, 120 hours Sequence B: pre-dose, 0.5, 2, 4, 24 hours Sequence C: pre-dose, 2, 3, 12, 24 hours	Sequence D: TBD Sequence E: TBD

Figure 1: Schema of Study 16-021

A detailed Schedule of Activities can be found in Protocol, Appendix A.

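### Cohort 1 AUC(0-last): on the natural reading, the linear trapezoidal rule overstates the area across the unsampled 24–120 h gap, or the area stops at 24 h; a minor point with a cheap SAP fix

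*Protocol*

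**What the plan says.** **Rule.** Protocol 8.1 (Pharmacokinetic Assessments) and the synopsis (Criteria for Evaluation) state that AUC(0-last) is "computed using the linear trapezoidal rule" and runs to the last concentration the assay can quantify. SAP 4.1 and 6.5.1 keep AUC(0-last) as a primary parameter. The SAP names no integration rule, no rule for samples below the limit and no fixed time window.

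**Sampling.** Cohort 1 has three patients on 40 mg, sampled at "Pre-dose, 0.5, 1, 2, 3, 4, 6, 12, 24, 120 hours" (protocol 3.1, Figure 1).

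**Whose AUC is individual.**
- Protocol synopsis, Criteria for Evaluation: parameters are "calculated by age group using POP PK methodology, except for patients with rich PK sampling".
- Protocol synopsis, Methodology: they are "determined per age group in a population PK type analysis except for those patients who have rich PK samples available for analysis".
- Protocol 10.6: "for each age group using POP PK methodology or for individual patients with rich PK sampling".
- SAP 3.1: "These will be estimated using POP PK methodology for age groups except the initial group of patients for which rich PK sampling is done".
- SAP 6.5.1 presents the primary parameters for individuals where it can, and rejects individual AUCs for patients with only five time points. In practice the individual AUCs are therefore those of Cohort 1.

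**Population PK.** Protocol 10.5 puts every patient's samples into the population PK analysis, Cohort 1 included. The lead-in to protocol 8.1 also places its whole parameter list under population PK.

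**What else is reported.** SAP 6.5.2 lists AUC(0-∞) and the other PK parameters but then cancels their analysis.

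**The concern.** Between 24 h and 120 h the concentration falls along a convex curve, and the linear rule replaces 96 hours of it with one straight line. The line lies above the curve, so the area is too large whenever the 120 h value is quantifiable. In the model below, that one trapezoid supplies 59% to 71% of the reported area.

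If the 120 h value is below the limit, the definition of AUC(0-last) ends the area at 24 h. A variable end time is inherent in this parameter, but here the two late sampling times are four days apart. A patient whose area ends at 24 h and one whose area ends at 120 h are not measured on the same scale, and no listing of end times is planned.

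With AUC(0-∞) dropped, AUC(0-last) is the only exposure area that will be reported. Cohort 1 supplies the only 40 mg data.

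**Working it through.** **The plan's own figure.** The plan gives no figure for integration error. Its related figure, 12 subjects in protocol 10.4, can be reproduced. The between-subject CV is 45% ("as measured by percent coefficient of variation was around 45" percent), so the log-scale SD is sqrt(ln(1 + 0.45²)) = 0.429. By simulation, a two-sided 90% t interval lies within 60–140% of the geometric mean with probability 80.1% at n=12 and 75.9% at n=11.

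**Inputs from the documents.** The Cohort 1 sampling times and the linear rule, as above. Protocol 1.0 reports "mean peak concentrations occurring 3 to 4 hours after oral administration" (adult data), so Tmax is set to 3.5 h, with 3 h and 4 h as checks.

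**Assumptions.** Half-lives of 20 to 60 h and a one-compartment shape. The documents state neither, and they give no assay limit.

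**Model.** C(t) = ka/(ka − k) × (e^(−kt) − e^(−ka·t)), with k = ln 2 / half-life and ka solved from Tmax = ln(ka/k)/(ka − k). The true area is the exact integral from 0 to 120 h.

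**Worked case, half-life 40 h.** k = 0.01733 and ka = 1.237, giving C(24) = 0.669 and C(120) = 0.127.
- Linear trapezoid for the gap: 96 × (0.669 + 0.127)/2 = 38.2.
- Exact area of the gap: (0.6691 − 0.1268)/0.01733 = 31.3, so the segment is 22% too large.
- True AUC(0-120) = 50.4 and linear AUC(0-120) = 57.3, an excess of 13.7%.
- Linear AUC(0-24) = 19.1, so ending at 120 h rather than 24 h multiplies the value by 57.3/19.1 = 3.0.

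Once absorption is over, the segment ratio is (x/2)·coth(x/2) with x = 96k. It depends on the half-life alone.

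| Assumed half-life (h) | Excess in gap segment | Excess in AUC(0-120) | C(120) as % of Cmax | Linear AUC(0-120) ÷ AUC(0-24) |
|---|---|---|---|---|
| 20 | 79% | 35.0% | 1.8% | 2.4 |
| 30 | 38% | 21.2% | 6.9% | 2.7 |
| 40 | 22% | 13.7% | 13% | 3.0 |
| 50 | 14% | 9.4% | 20% | 3.2 |
| 60 | 10% | 6.8% | 26% | 3.4 |

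Setting Tmax to 3 h or 4 h moves the AUC(0-120) excess by at most 0.3 points.

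**With linear-up/log-down trapezoids.** The one-compartment error falls to between −0.2% and −0.1%.

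**Two-phase sensitivity.** 45 assumed shapes were tried: distribution half-life 3, 5 or 8 h; terminal half-life 20 to 60 h; terminal coefficient 10, 20 or 30%; Tmax 3.5 h. The linear rule gives +8% to +45% and log-down gives +1% to +14%.

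**Scale of sampling error at n=3.** On the log scale the standard error is 0.429/√3 = 0.248, or about 28%. SAP 6.1 plans a mean with a 95% CI. At a 45% CV its half-width is 4.30 × 45%/√3, about 112% of the mean.

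**The case against.** **Use of the rule is an inference.** The protocol 8.1 lead-in covers its list with population PK, and SAP 6.1 makes the SAP govern all analyses, yet the SAP names no AUC rule. This stands in part. The linear trapezoid is still the only AUC rule in either document, and the synopsis states it under a lead-in that exempts the rich-sampled patients. A reader might also infer that Cohort 1 is left out of the population PK analysis. Protocol 10.5 says otherwise: those patients are only spared having their parameters derived solely at group level.

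**The two problems exclude each other within a profile.** This stands. A profile has either the integration excess or the early end, not both. The 35% figure needs an assay that reads about 2% of Cmax, and at that half-life an early end is more plausible. Nor can unequal end times be called the larger problem at 40 to 60 h. There C(120) is 13% to 26% of Cmax and so the most likely to be measured, in which case all three areas end at 120 h.

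**The size is small against n=3, and little depends on it.** This stands. An excess of 7% to 14% is well inside a 28% standard error. No hypothesis is tested, and Part 2 was cancelled, so no dose for younger children will be derived from these values. What remains is that sampling error shows in a confidence interval, whereas a one-directional integration bias or an unlisted end time does not.

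**Cohort 2.** A reader might carry the error over to Cohort 2. The documents support that only if a trapezoid is run on the average profile; a population model would not have this error. How the SAP's averaging fits with its population PK wording is a separate question.

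**Conclusion.** The point holds as a minor one. On the natural reading, the stated rule biases the Cohort 1 individual AUC(0-last) upward whenever the 120 h sample is quantifiable. The direction follows from convexity and does not depend on the half-life. The size does: about 7% at 60 h, 14% at 40 h and 35% at 20 h, given one compartment and Tmax 3.5 h. None of these is an expected value for this trial.

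For a profile whose 120 h sample is below the limit, the integration error is absent. Its area is then smaller by a factor of about 2.4 to 3.4 than one carried to 120 h in the same model. This is more plausible at shorter half-lives, and how likely it is cannot be judged without the assay limit.

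The consequence is confined to descriptive primary values in three patients. The documents do not support a claim that the trial's conclusions or any later dose are compromised.

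**What to change.** In SAP 6.5.1, with the change recorded in SAP 6.11:

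1. State that Cohort 1 individual AUC(0-last) uses linear trapezoids while concentrations rise and logarithmic trapezoids while they fall. Apply the same rule to any Cohort 2 average profile that is integrated by trapezoid.
2. List the last quantifiable time beside each AUC(0-last).
3. Report AUC(0-24) for each Cohort 1 patient as a common-window measure. For Cohort 2 it can come only from the average profile or the model, because Sequence A has no 24 h sample.

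Item 1 does not cure unequal end times, so items 2 and 3 are needed as well.

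**Cost.** A few lines of SAP text, one software option and two listing columns, with no new data. The downside is one extra reported measure. Log-down also assumes log-linear decline across the gap, which left up to about 14% excess in the two-phase shapes tried.
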